#### 6.11.6. Secondary Health Outcomes Analyses

For the Insulin Treatment Satisfaction Questionnaire (ITSQ), the change from baseline to LOCF endpoint while on treatment in each domain transformed score (inconvenience, lifestyle, hypoglycemic control, glycemic control, delivery system) and overall transformed score will be analyzed using the ANCOVA model with strata (country, type of basal insulin, use of metformin at study entry and HbA1c stratum), and treatment as fixed effects and baseline as a covariate.

#### 6.11.7. Analyses of Exploratory Objectives

Summary statistics, including number of patients and proportion of categorical outcomes (5 levels) for the 5 dimensions (mobility, self-care, usual activity, pain/discomfort, and anxiety/depression) of the European Quality of Life – 5 Dimensions 5 Level (EQ-5D-5L) will be provided by visit and by treatment. The change from baseline to LOCF endpoint (Week 26, Visit 18) in the EQ-5D-5L United Kingdom (UK) population-based health state index score and EuroQol visual analogue scale (EQ-VAS) score will be analyzed using the ANCOVA model CC

For the Work Productivity and Activity Impairment General Health (WPAI-GH), the change from baseline to LOCF endpoint in each score (absenteeism, presenteeism, work productivity loss, and activity impairment) will be analyzed using the ANCOVA model similar to ITSQ.

Within-day and between-day glycemic variability measured by the standard deviation (SD) and the coefficient of variation (CV) of 10-point SMBG profiles will also be analyzed by MMRM model specified in Section 6.11.5. At a given visit, the CV and SD on each day with a valid SMBG profile will be calculated using all the glucose values within that day, then the average values of these CVs and SDs will be used as the within-day CV and SD at that visit in analysis. At a given visit, the CV and SD at each of the 10 pre-specified SMBG time points will be calculated using the corresponding glucose values of the valid SMBG profiles, then the average values of these CVs and SDs will be used as the between-day CV and SD at that visit in analysis.

Table 6.3. lists additional variables for potential exploratory analyses.

Table 6.3. Additional Exploratory Efficacy Variables

Variable Description	Derivation	Statistical Method
Incremental areas under the serum	iAUC+: the total area under the serum glucose	ANCOVA
glucose concentration-time curve	curve but above the glucose level at time 0 when	
from 0 to 30 minutes, 0 to 1 hour,	the meal starts for the MMTT within the specific	
0 to 2 hours, 0 to 3 hours, and 0 to	time frame. The area will be calculated by	
4 hours after the meal in MMTT.	trapezoids rule.	
Area under/above the serum	AUC: Total area under the serum glucose	ANCOVA
glucose concentration time curve	curve calculated by trapezoids area within	
from 0 to 30 minutes, 0 to 1 hour, 0	the specific time frame	
to 2 hours, 0 to 3 hours, and 0 to 4		
hours after the meal in MMTT.		

	
 
AUC>180: Total area under the serum glucose curve but above the 18 0mg/dL level within the specific time frame
 
AOC≤70: Total area above the serum glucose curve but below the 70 mg/dL level within the specific time frame.
 
	
Glucose variability during MMTT	
 
The CV of all serum glucose values collected during the MMTT
 
The SD of all serum glucose values collected during the MMTT.
 
	ANCOVA
1-hour and 2-hour PPG excursions and daily mean by 10-point SMBG profile	
 
The difference in means between 1-hour PPG and fasting PG at the same visit
 
The difference in means between 2-hour PPG and fasting PG at the same visit
 
The average of daily means at the same visit
 
	MMRM
Incidence of HbA1c ≤6.5% and <7.0% without severe hypoglycemia	
 
Binary indicator with 1 indicating HbA1c ≤6.5% at Week 26 and no severe hypoglycemia during 0-26 weeks of treatment
 
Binary indicator with 1 indicating HbA1c <7% at Week 26 and no severe hypoglycemia during 0-26 weeks of treatment.
 
	Logistic regression

Abbreviations: ANCOVA = analysis of covariance; AOC = area over the curve; AUC = area under the curve; CV = coefficient of variation; iAUC = incremental area under the curve; HbA1c = hemoglobin A1c; MMRM = mixed-meal tolerance test; MMTT = mixed-meal tolerance test; PG = plasma glucose; PPG = postprandial glucose; SD = standard deviation; SMBG = self-monitored blood glucose.

#### 6.12. Safety Analyses

Safety measures will include AEs, hypoglycemia, vital signs and weight, treatment exposure, laboratory measures, and antibodies to insulin lispro. Refer to Table 6.1 and Table 6.2 for the analysis population and the baseline definition used in the analysis of a safety measurement for a specific study period.

#### 6.12.1. Extent of Exposure

Duration of exposure to IP will be summarized. The following summary statistics will be provided: n, mean, SD, median, minimum, maximum, and sum (that is, total patient-years of exposure). The number and proportion of patients falling into the following different exposure categories will also be summarized: <1 month (>0 and <30 days),  $\geq$ 1 and <3 months ( $\geq$ 30 and <90 days),  $\geq$ 3 and <6 months ( $\geq$ 90 days and <180 days) and  $\geq$ 6 months ( $\geq$ 180 days).

Patients who complete the study treatment period are required to complete a safety follow-up visit without study drug; and patients who discontinue the IP prematurely are encouraged to remain in the study without study drug. The days on study after discontinuing IP, and the days on study from date of first study drug to the last study visit date up to Visit 801 will also be summarized.

#### 6.12.2. Adverse Events

Analyses of AEs will include 2 sets of analyses, unless otherwise specified. The first set of analyses will include data prior to discontinuation of IP. The second set of analyses will include all data in the corresponding analysis period regardless of IP use.

Events that are newly reported after the first dose of prandial insulin provided as study drug (that is, open-label insulin lispro used during the lead-in period or IP used during the treatment period) or reported to worsen in severity from baseline (defined in Table 6.2) will be considered TEAEs. The MedDRA Lowest Level Term (LLT) will be used in the treatment-emergent assessment. The maximum severity for each LLT during the baseline period will be used as baseline severity. For events occurring on the day of first dose of bolus insulin provided by this study, the case report form (CRF)-collected flag will be used to determine whether the event started or worsened post-treatment.

In an overview table, the number and percentage of patients who experienced a TEAE, experienced a serious adverse event (SAE), died due to an AE, discontinued from study due to an AE, or discontinued IP due to an AE will be summarized by treatment group.

The number and percentage of patients with TEAEs will be summarized by treatment using MedDRA PT nested within SOC. Events will be ordered by decreasing frequency within SOC. As an additional table, the percentages of patients with TEAEs will be summarized by treatment using MedDRA PT (without regard to SOC). Events will be ordered by decreasing frequency. Statistical comparisons will be applied at both the SOC and PT levels. Fisher's exact test will be performed for treatment comparison.

The number and percentage of patients with TEAEs by maximum severity will be summarized by treatment using MedDRA PT (without regard to SOC) and data collected prior to discontinuation of IP. For each patient and TEAE, the maximum severity for the MedDRA PT is the maximum postbaseline severity observed from all associated LLTs mapping to the MedDRA PT. No statistical comparison between treatment groups will be conducted.

The number and percentage of patients with common TEAEs (defined as  $\geq$ 5% before rounding in LY900014-treated patients) will be summarized by treatment group using MedDRA PT (without regard to SOC). Events will be ordered by decreasing frequency. Treatment will be compared by Fisher's exact test.

The number and percentage of patients who experienced an SAE, including deaths and SAEs temporally associated or preceding deaths, will be summarized by treatment group using MedDRA PT (without regard to SOC). Events will be ordered by decreasing frequency. A listing of all SAEs will also be provided.

The number and percentage of patients who discontinued from study due to an AE will be summarized by treatment group using MedDRA (without regard to SOC) using all data regardless of IP use. The number and percentage of patients who discontinued IP due to an AE will be also summarized by treatment group using MedDRA PT (without regard to SOC) using data prior to discontinuation of IP. Events will be ordered by decreasing frequency. A listing of all AEs as reason for study or IP discontinuation will also be provided.

The number and percentage of patients who experienced other notable TEAEs (potential systemic hypersensitivity reaction, injection site reaction, and hepatic disorder) will be summarized by treatment group using all TEAEs regardless of IP use.

For events that are gender-specific (as defined by MedDRA), the denominator and computation of the percentage will include only patients from the given gender.

Table 6.4 summarizes the planned analyses and the requirement of analysis data for different analysis periods. A 'Yes' in the IP USE column indicates that only data collected prior to discontinuation of IP will be included.

Analysis Period	Analysis Population	Analysis	IP USE	Treatment
Lead-in Period	All enrolled patients	AE overview; TEAE by PT, SAE, discontinuation from study due to AE	N/A	Open-label insulin lispro
Treatment Period (0-26 Weeks)	All patients in safety population	AE overview; TEAE by SOC and by PT; common TEAE; TEAEs by maximum severity; SAE; discontinuation from IP due to AE	Yes	LY900014, insulin lispro,
Week 0 – Visit 801	All patients in safety population	AE overview; TEAE by SOC; common TEAE; SAE; other notable AEs; study discontinuation due to AE	All data regardless of IP use	LY900014, insulin lispro

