#### 6.15. Clinical Trial Registry Analyses

Additional analyses will be performed for the purpose of fulfilling the Clinical Trial Registry (CTR) requirements.

Analyses provided for the CTR requirements include the following:

- Summary of AEs, provided as a dataset which will be converted to an XML file. Both Serious Adverse Events and 'Other' Non-Serious Adverse Events are summarized by treatment group and MedDRA PT.
- An AE is considered 'Serious' whether or not it is a TEAE.
- An AE is considered in the 'Other' category if it is both a TEAE and is not serious. For each Serious AE and 'Other' AE, for each term and treatment group, the following are provided:
  - the number of participants at risk of an event
  - the number of participants who experienced each event term
  - the number of events experienced.
- Consistent with www.ClinicalTrials.gov requirements, 'Other' AEs that occur in fewer than 5% of patients/subjects in every treatment group may be excluded if a 5% threshold is chosen. Allowable thresholds include 0% (all events), 1%, 2%, 3%, 4%, and 5%.
- Adverse event reporting is consistent with other document disclosures for example, the CSR, manuscripts, and so forth.

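### The common TEAE table picks its terms on the LY900014 rate alone and then compares the arms: a minor presentation bias that a one-phrase change removes

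*SAP*

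**What the plan says.** SAP 6.12.2 (Adverse Events) defines a common TEAE by a frequency of at least "5% before rounding in LY900014-treated patients) will be summarized by treatment group using MedDRA PT". No frequency on insulin lispro is mentioned. For the terms so chosen, "Treatment will be compared by Fisher's exact test".

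Table 6.4 in the same section plans this table twice:
- Weeks 0 to 26, on investigational product (IP): "AE overview; TEAE by SOC and by PT; common TEAE; TEAEs by maximum severity; SAE; discontinuation from IP due to AE".
- Week 0 to Visit 801, regardless of IP use: "AE overview; TEAE by SOC; common TEAE; SAE; other notable AEs; study discontinuation due to AE".

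Section 6.12.2 also plans tables with no frequency cut-off. TEAEs are summarized by preferred term (PT) nested within system organ class (SOC), and "As an additional table, the percentages of patients with TEAEs will be summarized by treatment using MedDRA PT (without regard to SOC)". For these, "Statistical comparisons will be applied at both the SOC and PT levels", again by Fisher's exact test.

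SAP 6.15 (Clinical Trial Registry Analyses) has a 5% rule for the registry's non-serious events that treats the arms alike: those "that occur in fewer than 5% of patients/subjects in every treatment group may be excluded if a 5% threshold is chosen".

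Protocol 10.3.4 sorts AE tables by frequency in the LY900014 group but sets no 5% cut-off.

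**The concern.** Both arms are active and double-blind, and comparing their safety is a stated objective (SAP Table 4.1, objective 12). The common TEAE table is a planned between-arm comparison, yet its rows are chosen on the observed rate in one of the two arms being compared. Two things follow.

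1. A term that is common only on insulin lispro is not listed, while its mirror image is listed and tested.
2. Among listed terms, a chance high on LY900014 is part of the entry condition and a chance high on lispro is not. The displayed difference then leans toward an LY900014 excess even when the true rates are equal.

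At stake is how fairly a short, easily quoted table represents the comparison. Neither the underlying data nor any formal conclusion is at risk.

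**Working it through.** **Plan figures.** The SAP gives no numerical property for this table, so there is none to reproduce. The only design input needed is the arm size. SAP 5.2 gives 298 completers, 15% dropout, about 350 randomized and 1:1 allocation: 298 / (1 − 0.15) = 350.6, which agrees with about 350, so about 175 per arm.

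**Assumptions.** The Safety population equals the randomized population (175 per arm). The arms are independent binomials. True term rates are assumed over a range, because the documents give none.

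**Entry count.** 5% before rounding is 0.05 × 175 = 8.75, so a term is listed when at least 9 LY900014 patients had it.

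**Formulas.** Write A for the LY900014 count, B for the lispro count and p for a true rate common to both arms.
- Share omitted among terms reaching 5% in at least one arm: P(A<9) × P(B≥9) / [1 − P(A<9) × P(B<9)].
- Mean LY900014 rate given listing: p × P(Bin(174, p) ≥ 8) / P(Bin(175, p) ≥ 9).
- Mean lispro rate given listing: p, because B plays no part in the selection.

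**Worked case, p = 5% in both arms.** P(A≥9) = 0.514 and P(A<9) = 0.486.
- Omitted share: 0.486 × 0.514 / (1 − 0.486²) = 0.250 / 0.764 = 0.327.
- Mean listed LY900014 rate: 0.05 × 0.6453 / 0.5136 = 6.28%, against 5.0% on lispro.

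**Range, equal true rates.**

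| True rate, both arms | P(listed) | Mean LY900014 rate if listed | Apparent excess (points) | Omitted share |
|---|---|---|---|---|
| 4% | 0.268 | 5.9% | +1.9 | 42% |
| 5% | 0.514 | 6.3% | +1.3 | 33% |
| 6% | 0.728 | 6.8% | +0.8 | 21% |
| 8% | 0.945 | 8.2% | +0.2 | 5% |
| 10% | 0.993 | 10.0% | +0.04 | 0.7% |

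At a true 5%, LY900014 is numerically higher in 70% of listed terms and lower in 21%. At 8% the split is 49% against 43%.

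**Nominal significance among listed terms, true 5% in both arms.** Fisher p<0.05 with an LY900014 excess: 2.6%. With a lispro excess: 0.01%. Without selection it is 1.3% in each direction.

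**Unequal true rates.** With 4% on LY900014 and 6% on lispro, P(A≥9) = 0.268 and P(B≥9) = 0.728. The omitted share is 0.732 × 0.728 / (1 − 0.732 × 0.272) = 0.67. For the mirror image (6% and 4%) it is 0.272 × 0.268 / (1 − 0.272 × 0.732) = 0.09.

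**Single-term examples.** 8/175 on LY900014 against 19/175 on lispro (4.6% and 10.9%) has two-sided Fisher p = 0.043. 3/175 against 12/175 has p = 0.031. Neither would be listed.

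**Sensitivity to arm size.** With 149 per arm (0.05 × 149 = 7.45, so at least 8 patients) and a true 5% in both arms, the apparent excess is +1.5 points and the omitted share is 35%.

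**Either-arm rule.** With 175 per arm and equal true rates, the mean listed difference is 0.00 points at every rate from 2% to 10%, and nominally significant results are equally likely in each direction. At a true 5% both listed means are 5.4%.

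**The case against.** The case for leaving the table alone is strong on weight.

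- **The terms are shown elsewhere.** The unrestricted tables in 6.12.2 carry every term with a Fisher test. The 8 against 19 example would appear there with the same p = 0.043. A reader might infer that events common only on lispro vanish from the report; they leave only this table. For Week 0 to Visit 801, Table 6.4 lists a table by SOC and no separate table by PT, but the text of 6.12.2 describes the SOC table as PT nested within SOC, so the terms should appear there too.
- **No test result changes.** A reader might infer that the rule creates false LY900014 signals. It does not: each term's p-value is the same with or without the cut-off. What changes is which terms sit side by side.
- **The lean is against the sponsor's product.** Any term at 5% or more on LY900014 is listed whatever the lispro rate, so a common LY900014 harm cannot be hidden.
- **SAP 6.15 is not contradicted.** Its rule is permissive, covers registry disclosure of non-serious events, and does not govern the study report tables. It shows a symmetric cut-off that the SAP already uses for another purpose, and no more than that.
- **The size depends on assumed rates near the cut-off**, and a symmetric rule does not give valid inference after selection. At a true 3% in both arms, an either-arm rule still gives nominal significance in 4.2% of listed terms per direction, against 1.0% unselected.

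All of this stands, and it limits the point to presentation. It does not justify the asymmetry itself: a table that tests two blinded active arms against each other has no stated reason to choose its rows from one of them, and the protocol does not require it.

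**Conclusion.** The listed subset is asymmetric, and the consequence is minor. Assuming 175 per arm, independent arms and a true 5% in both, listed terms average 6.3% on LY900014 against 5.0% on lispro, and 33% of the terms reaching 5% in either arm are left off. The lean is material for true rates up to about 6% and negligible by 8% to 10%. The true rates are assumptions throughout.

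The documents do not support reading this as lost safety data, as an error in any individual test, or as a conflict between 6.12.2 and 6.15. SAP 6.5 applies no multiplicity adjustment outside the primary and multiplicity-adjusted objectives, so these safety tests are unadjusted. No primary or multiplicity-controlled conclusion uses this table.

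**What to change.** In SAP 6.12.2, change the common TEAE definition so that the 5% cut-off (before rounding) is met in either treatment group instead of among LY900014-treated patients only. Apply it to both common TEAE entries in Table 6.4 (Weeks 0 to 26 on IP, and Week 0 to Visit 801). Add a sentence saying that p-values in this frequency-selected table are descriptive, since symmetry removes the directional lean but not the effect of selecting on observed frequency.

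The cost is one phrase and one sentence in the SAP and one program condition, to be settled before unblinding. The downside is a few more rows in two tables. No extra data or patients are needed.

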7.2.1.5. Transitioning off Study Insulin Therapy

Patients should take their last dose of study insulin (LY900014 or insulin lispro) at Visit 18 with the MMTT if performed the same date as Visit 18 or the evening the day prior to Visit 18 if the MMTT is performed prior to Visit 18 or at early discontinuation.

No special instructions for transition to nonstudy prandial insulin are necessary for patients who were using basal bolus therapy prior to study entry. After completion of study treatment, these patients will restart the prandial insulin therapy used prior to study entry or may transition to a rapid-acting insulin analog other than insulin lispro if the patient was treated with regular human insulin prestudy. Patients may remain on the basal insulin used during the study (if it was changed at Visit 2) at the discretion of the investigator or return to their prestudy basal insulin.

Patients who were using premixed insulins prior to study entry may choose to stay on basal bolus regimen at the discretion of the investigator. However, patients who were not on lispro product prior to entry should NOT use lispro product during the safety follow-up period.

Additional guidance for insulin therapy after the treatment period is provided in Section 7.8.2.

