10.3. Statistical Analyses

10.3.1. General Statistical Considerations

Statistical analysis of this study will be the responsibility of Lilly or its designee. Any change to the data analysis methods described in the protocol will require an amendment ONLY if it changes a principal feature of the protocol. Any other change to the data analysis methods described in the protocol, and the justification for making the change, will be described in the SAP or the clinical study report (CSR). Additional exploratory analyses of data will be conducted as deemed appropriate.

The primary analysis is for the treatment period through Week 26. The primary endpoint is the HbA1c measurement obtained at Week 26 (Visit 18).

Efficacy analyses will be conducted on all randomized patients using an intention-to-treat (ITT) approach according to the treatment the patients are assigned. Efficacy analyses, including the analyses for the primary and multiplicity adjusted objectives, will include data collected prior to permanent discontinuation of IP through Week 26. When change from baseline is included as a response variable of analysis models, the patient will be included in the analysis only if he/she has a baseline and a postbaseline measurement. Selected efficacy analyses will also be conducted using the Per-Protocol (PP) and Completer populations.

Safety analyses will be conducted on the Safety population. Analyses of AEs will include 2 sets of analyses, unless otherwise specified. The first set of analyses will include data collected prior to permanent discontinuation of IP. The second set of analyses will include all data collected during the course of the entire study regardless of IP use. Analyses of hypoglycemia will be conducted on data collected prior to permanent discontinuation of IP, while analyses for post-treatment may be conducted as needed. Analyses of safety laboratory measurements will be performed on all data collected during the planned treatment period regardless of IP use. Week 26 analyses will include treatment comparisons between the 2 treatment groups.

Unless otherwise noted, all tests of treatment effects will be conducted at a 2-sided alpha level of 0.05, and CIs will be calculated at 95%, 2-sided. All tests of interactions between treatment groups and other factors will be conducted at a 2-sided alpha level of 0.10.

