#### 6.12.4. Hypoglycemic Events and Other Adverse Events

The analysis plans for the following adverse events are discussed in Section 6.12.4.1 through Section 6.12.4.4:

- hypoglycemic events
- systemic hypersensitivity reaction
- injection site reaction
- hepatobiliary events

These AE analyses will be similar to the TEAE analyses. Refer to Table 6.4 for the requirement of analysis data for a specific analysis period.

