#### 6.12.4.3. Injection Site Reaction

The injection site reactions will be searched by MedDRA PTs from all TEAEs. The number and percentage of patients experiencing treatment-emergent injection site reaction will be summarized and compared by treatment group using Fisher's exact test.

For injection site reactions, the presence and severity of erythema, induration, pain, pruritus, and edema were collected through the eCRF, and will be summarized for each treatment. There will be no statistical comparison between treatments.

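### The grouped injection-site reaction search has no on-IP analysis: it runs only from Week 0 to Visit 801 regardless of IP use, so local reactions after IP stops count for the randomized arm

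*SAP*

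**What the plan says.** Both documents set a default for adverse events. The SAP (6.12.2) states: "Analyses of AEs will include 2 sets of analyses, unless otherwise specified". Protocol 10.3.1 carries the same qualifier and adds: "The first set of analyses will include data collected prior to permanent discontinuation of IP". The second set takes all data regardless of IP use.

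SAP 6.12.2 then makes an exception for potential systemic hypersensitivity, injection site reaction and hepatic disorder, which "will be summarized by treatment group using all TEAEs regardless of IP use". Table 6.4 agrees with that exception:

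- Treatment Period (0-26 Weeks), on-IP data only: "AE overview; TEAE by SOC and by PT; common TEAE; TEAEs by maximum severity; SAE; discontinuation from IP due to AE".
- Week 0 to Visit 801, all data: "AE overview; TEAE by SOC; common TEAE; SAE; other notable AEs; study discontinuation due to AE".

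SAP 6.12.4, which introduces the detailed sections, sends the reader back to that table: "Refer to Table 6.4 for the requirement of analysis data for a specific analysis period". SAP 6.12.4.3 sets no time limit of its own: "The injection site reactions will be searched by MedDRA PTs from all TEAEs". It plans numbers, percentages and Fisher's exact test.

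The Visit 801 window includes time on other products. SAP 6.12.1 describes the follow-up visit as taking place without study drug. Protocol 7.2.1.5 has former basal-bolus patients go back to their pre-study prandial insulin and says that "patients who were not on lispro product prior to entry should NOT use lispro product during the safety follow-up period". Under Protocol 5.3.1, patients who stop IP early but remain in the study are followed through Visit 801.

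**The concern.** Protocol 5.5 gives LY900014 the same lispro concentration as the marketed product, and Protocol 3.2 attributes its different profile to added treprostinil and citrate, with treprostinil acting by local vasodilatation. Local reactions are therefore a natural place for a formulation difference to appear.

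Once IP stops, a new reaction at an injection site cannot be a reaction to a current injection of IP. Adding a similar number of such events to both arms raises both incidences and pulls their ratio toward 1. Nothing planned would show a reader how many patients with a grouped reaction had it while on IP. The on-IP tables by preferred term do not supply that count, because one patient may appear under several terms. The system organ class is too coarse, because it mixes these reactions with unrelated events.

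**Working it through.** **1. Which analyses exist on IP.** The plan states no figure for this point, so there is none to reproduce. Comparing the parts of the SAP:

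| Level of injection-site information | On-IP result planned? | All-data result planned? |
|---|---|---|
| Single preferred terms | Yes, with Fisher's exact test | In part (common TEAEs; TEAEs by SOC) |
| Whole system organ class | Yes, with Fisher's exact test | Yes |
| Grouped preferred-term search (6.12.4.3) | No | Yes, with Fisher's exact test |

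Only the grouped search lacks an on-IP result. SAP 6.1 already defines on-IP data for adverse events: an event date no later than the last dose date plus 1 day.

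**2. Share of the window that is off IP.** Inputs: 26 weeks of treatment and 4 of follow-up (SAP 5.1); 15% dropout and 350 randomized, so 175 per arm (SAP 5.2).

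- Completer: 4 / (26 + 4) = 13.3%.
- Assume that the 15% stop IP at Week 13 and stay to Week 30: (0.85 × 4 + 0.15 × 17) / 30 = 5.95 / 30 = 19.8%.
- Assume instead that they leave after 4 weeks of follow-up: 4 / (0.85 × 26 + 0.15 × 13 + 4) = 4 / 28.05 = 14.3%.
- With stopping between Weeks 4 and 22, under either pattern, the share is about 14% to 24%.

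**3. Effect on the comparison.** All event rates are assumed, because the documents give none. Let p be the on-IP incidence. Assume that the off-IP rate in both arms equals the on-IP lispro rate, so the added incidence is b = p(lispro) × off-IP weeks / 26. The observed incidence is then about p + b. Power is by exact enumeration of the two-sided Fisher test at 0.05 with 175 per arm.

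| On-IP incidences | Off-IP weeks | b | Observed | Ratio | Difference | Fisher power |
|---|---|---|---|---|---|---|
| 4% vs 1% | 0 | 0 | 4.00% vs 1.00% | 4.0 | 3.0 points | 29.7% |
| | 4 | 1% × 4/26 = 0.15% | 4.15% vs 1.15% | 3.6 | 3.0 points | 28.3% |
| | 5.95 | 1% × 5.95/26 = 0.23% | 4.23% vs 1.23% | 3.4 | 3.0 points | 27.6% |
| 6% vs 2% | 0 | 0 | 6.00% vs 2.00% | 3.0 | 4.0 points | 37.3% |
| | 4 | 2% × 4/26 = 0.31% | 6.31% vs 2.31% | 2.7 | 4.0 points | 35.1% |
| | 5.95 | 2% × 5.95/26 = 0.46% | 6.46% vs 2.46% | 2.6 | 4.0 points | 34.2% |

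The exact combination 1 − (1 − p)(1 − b) changes little: 4% vs 1% with 4 off-IP weeks gives a ratio of 3.60 and a difference of 2.995 points.

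**4. How far it could go.** With 6% vs 1% on IP, b = 0.25% takes the ratio from 6.0 to 5.0 and power from 66% to 62%. With b = 1%, they are 3.5 and 52%. But 1% in 4 weeks, against 1% in 26 weeks on lispro, is a weekly rate 26/4 = 6.5 times as high, and nothing in the documents suggests that. Even then the difference moves only from 5.0 to 4.95 points.

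**The case against.** **The choice is allowed.** A reader might infer that the SAP departs from the protocol. It does not. Both documents qualify the two-set rule, and the SAP then specifies otherwise in plain terms. This stands: the point is an improvement, not an inconsistency.

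**On-IP grouped results already exist.** A reader might infer that there is no grouped on-IP test at all. That is too strong, because the on-IP row includes the system organ class level and 6.12.2 tests at that level. What remains is the narrower gap: the injection-site search itself has no on-IP version.

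**The harm falls on a statistic that is not planned.** SAP 6.12.4.3 plans percentages and Fisher's exact test, not a relative risk, and the risk difference hardly changes. This stands and keeps the weight low. Readers may still form the ratio from the reported percentages, and the test loses a little power.

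**Attribution is not clean on IP either.** Basal insulin is injected throughout, so an on-IP cut does not isolate the prandial product. Patients on lispro before entry may restart it, and the study basal insulin may continue. The documents therefore do not support a claim that most off-IP reactions are to a different product. They support only that such reactions are not to a current injection of IP.

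**The same argument might seem to reach systemic hypersensitivity.** It does so only weakly. Onset may be delayed, and a cut at last dose plus 1 day would miss a reaction that appears two days after stopping. SAP 6.12.4.2 also plans a further summary of events that the investigator considers possibly related. That summary filters by judgement and not by time, but it does address attribution. No such summary is stated for injection site reactions. Delayed onset likewise supports the all-data analysis for hepatic disorders.

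**Conclusion.** The point holds for grouped injection-site reactions, as a minor gap in a permitted analysis choice. At least 13% of a completer's window is off IP, and about 14% to 24% overall if 15% stop early, depending on when they stop and whether they stay. Under the assumed rates in the main table, the ratio is slightly diluted (4.0 to between 3.6 and 3.4; 3.0 to between 2.7 and 2.6) and Fisher power falls by about 1 to 3 points from a base of 30% to 37%. The risk difference is essentially unchanged. These sizes rest on assumed incidences and on an off-IP rate equal to the lispro rate in both arms. The documents do not support a stronger conclusion, such as a breach of the protocol, a materially misleading comparison, or a reason to replace the all-data analyses of hypersensitivity or hepatic events. The point concerns reporting only and touches no dosing or patient-care rule.

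**What to change.** In SAP Table 6.4, add grouped injection-site reactions to the Treatment Period (0-26 Weeks) row with IP USE = Yes. Use the preferred-term search and Fisher's exact test of 6.12.4.3 and the on-IP rule of 6.1 (event date up to last dose date + 1 day). Amend the sentence in 6.12.2 to match, and keep the Week 0 to Visit 801 analysis beside the new one.

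For systemic hypersensitivity, an on-IP table may be added as a companion only; the all-data analysis should stay as planned. Leave hepatic disorders unchanged.

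The cost is one or two more tables, made from dates already collected, searches already specified and a window rule already in the SAP.
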